Through extensive in-silico testing, a proprietary bolus calculator has been developed by Insulet and is embedded in the Omnipod Horizon™ system. The bolus calculator can import CGM and trend as long as the pod has an available CGM value. A 3-month outpatient pivotal trial of Omnipod Horizon™ is currently underway however, it is expected that users will primarily use the system in Automated Mode. This study is designed to evaluate the safety and effectiveness of Omnipod Horizon™ System CGM-informed bolus calculator during Manual Mode operation. These data will supplement the extensive in-silico analysis to support safety and effectiveness of the Omnipod Horizon bolus calculator in clinical use.

Training and operation of the Omnipod Horizon™ System is identical in order to use the product with CGM informed Manual Mode or Automated Mode i.e. it is not possible to disable the Automated Mode functionality and still enable CGM integration. Therefore, this clinical protocol is similar to protocols under IDE G190267 and G190270.

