In Automated Mode, the system will support the use of multiple target glucose values, currently intended to be 110-150 mg/dL at commercialization, in 10 mg/dL increments. The experience for the user will reflect current setup flows whereby the health care provider assists the user to program basal rates, glucose targets and bolus calculator settings. These in turn will inform the MPC algorithm for insulin dosing parameters. The insulin dosing parameters will be adapted over time based on the total daily insulin (TDI) delivered during each Pod use. A temporary hypoglycemia protection mode (Hypo Protect) may be implemented by the user for various time durations during Automated Mode. With Hypo Protect, the algorithm reduces insulin delivery and is intended for use over temporary durations when insulin sensitivity is expected to be higher, such as during exercise.

In this study, participants will be instructed to NOT use Automated Mode. This study will be restricted to Manual Mode operation ONLY.

The Omnipod Horizon™ System will include two apps on a locked-down smartphone (Samsung J3), referred to as Personal Diabetes Manager (PDM): the Horizon™ App and the Dexcom App. The Horizon™ App, which will have a similar interface to the cleared Omnipod® DASH System (K191679), will allow the use of large text, graphics, and on-screen instructions to prompt the user through set-up processes. It will also be used to program the user's custom basal insulin delivery profile, check the Pod status, initiate bolus doses of insulin, make changes to a patient's insulin delivery profile, handle system alerts and alarms, and enter Automated Mode.

The Dexcom App interface is identical to the current app of the interoperable Dexcom G6 Continuous Glucose Monitoring System (K191450) and will provide CGM data, alerts, and alarms to the user.

The Horizon™ App and Dexcom App will not directly communicate with one another. Instead, the iCGM transmitter will communicate EGV (estimated glucose values) directly to the Pod. The Dexcom transmitter number must be entered into the Horizon™ App, and this information is sent to the Pod to allow transmission of EGV. The Pod will pair directly to the transmitter to receive EGV for the algorithm and also sends the EGV back to the Horizon™ App as shown in **Figure 1**.

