- Data review by clinician to ensure that subject is delivering boluses as instructed during Visit 2

8.2 Phase 2

8.2.1 Visit 4

Visit 4 will be conducted either over the telephone or in person at the clinical site on Day 8 ± 1 d. This visit will mark the start of Phase 2, which is 7-days of Manual Mode with a connected CGM using the CGM-informed bolus calculator to deliver boluses. This visit will include:

- Review of concomitant medications
- Assessment of adverse events
- Pairing the CGM transmitter to the Horizon App on the PDM
- Assessment of complaints and/or device deficiencies
- Data review by clinician to ensure that subject was delivering boluses as instructed during Visit 2.
- Upload BG and ketone meter data (if visit is conducted in person at the clinical study site)

During this visit subjects will be instructed to:

- Use the CGM-informed bolus calculator to administer meal boluses for all meals when carbohydrates are consumed as well as to administer correction boluses, when desired. For meal boluses, subjects will estimate the grams of carbohydrates for each meal, enter the carbohydrate estimate into the bolus calculator, choose 'Enter CGM' to populate the bolus calculator and administer their meal bolus. For correction boluses, subjects will choose 'Enter CGM' to populate the bolus calculator and administer their correction bolus. The timing of the bolus delivery will be per each subject's typical dosing routine.
- Consume meals and snacks of their own choosing.
- Subjects may adjust their basal rates or use advanced features such as Temp Basal and Extended Bolus per usual
- Follow their pre-exercise management such as insulin reduction for meal boluses, consumption of snacks, or adjusting their insulin delivery settings
- Treat themselves per their usual routine if they become hypoglycemic or hyperglycemic or have symptoms of either at any time during the study
- Change their CGM per manufacturer's instructions or sooner if necessary
- Change the Pod at least once every 72 hours
- For subjects aged 2-5.9 years of age, parents or trained caregivers will be instructed that they need to be physically present during the decision and delivery of insulin boluses for this age group, as well as be available for glucose monitoring and treatment during the 4-hour post bolus period.

8.2.2 Visit 5

Visit 5 will be conducted either over the telephone or in person at the clinical study site on Day 10 ± 1 d. This visit will include:

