8.2.3 Visit 6 (End of Study)

Visit 6 will be conducted either over the telephone or in person at the clinical study site on Day 14 ±1d. This visit will include:

- Review of concomitant medications
- Assessment of vital signs (if visit is conducted in person at the clinical study site)
- Assessment of adverse events
- Return of devices (if not commencing or recommencing their participation in the Omnipod Horizon™ Pivotal Study (G190270). Subjects aged 2-5.9 may hold onto their devices if continuing onto the Pivotal study, but must return to using their standard therapy for the Pivotal study Standard Therapy Phase.)
- Assessment of complaints and/or device deficiencies
- Data review by clinician to ensure that subject was delivering boluses as instructed during Visit 4
- Upload BG and ketone meter data (if visit is conducted in person at the clinical study site)

This visit will mark the end of this study for each subject.

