11.4.3 PP (Per-Protocol) Analysis Set

The Per-Protocol (PP) analysis set is a subset of the mITT analysis set. Subjects will be included in the PP analysis set if they have a minimum of 80% system use (approximately 5.6 days) during Phase 2 of the study without major protocol deviations. The PP analysis set will be used as supportive analysis for the endpoints. The following will be considered major protocol deviations:

- Major inclusion/exclusion criterion deviation
- Significant protocol non-compliance that may confound the study objective data (e.g., use of prohibited medications)

The list of subjects excluded from the PP analysis set will be determined prior to analysis. If the PP analysis set does not differ from the mITT analysis set, separate analyses will not be presented.

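### Is the per-protocol rule of 80% system use (about 5.6 days) in Phase 2 at odds with the visit days and too loosely defined to apply?

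*Combined protocol and SAP*

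**What the plan says.** Section 11.4.3 makes the PP set a subset of the mITT set. Its one numeric criterion is a "minimum of 80% system use (approximately 5.6 days) during Phase 2 of the study without major protocol deviations". Major deviations are of two kinds: eligibility breaches, and significant non-compliance that could confound the study data, with prohibited medication given as an example. The exclusion list is settled before analysis. PP results are supportive, and they are not shown separately if the set equals mITT. Section 11.4.2 makes mITT primary.

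On the length of Phase 2, Section 8.2.1 says "Visit 4 will be conducted either over the telephone or in person at the clinical site on Day 8", with a window of one day either side, and adds: "This visit will mark the start of Phase 2, which is 7-days of Manual Mode with a connected CGM". Section 8.2.3 places Visit 6 "in person at the clinical study site on Day 14", with the same window, and says: "This visit will mark the end of this study for each subject". Section 8.1.1 puts Visit 2 on Day 1 and describes the study as lasting 14 days.

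On the device, the Introduction says: "The bolus calculator can import CGM and trend as long as the pod has an available CGM value". It also says that "it is not possible to disable the Automated Mode functionality and still enable CGM integration". Section 2.1.1 answers with: "This study will be restricted to Manual Mode operation ONLY". Section 8.1.1 makes any Automated Mode use a protocol deviation, and Section 13.7 requires deviations to be documented and explained in the eCRF. Section 11.5.1 removes only CGM records that carry no glucose value.

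Sections 11.2 and 11.5 describe a non-powered study with no hypotheses, whose endpoint results will not support clinical claims.

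**The concern.** Four features make the criterion look defective.

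- **Two forms of one threshold.** The rule is given as a percentage and as a number of days. Subtracting Day 8 from Day 14 gives 6 days, not 7, and the windows stretch or shrink that further. A subject who used the system throughout a short Phase 2 would pass on 80% and fail on 5.6 days.
- **No definition of system use.** Wearing the Pod and having a connected CGM are different things, and the calculator under test needs the second. The text names no numerator, denominator or data source.
- **Automated Mode.** It cannot be switched off once the CGM is connected, and the PP text does not name it. Read literally, hours in Automated Mode could count as system use. Since Section 11.5.1 keeps every record with a glucose value, PP is the only planned analysis that could leave such hours out.
- **Phase 2 only.** Every endpoint compares Phase 2 with Phase 1, but the use criterion covers Phase 2 alone.

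At stake is the plan's only adherence-based check on the primary comparison. In cohorts of 5, 10 and 15, one subject is 20%, 10% or 6.7% of the set. Whether PP differs from mITT also decides whether PP results appear at all.

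**Working it through.** **1. The plan's own figure.** Inputs: 80% (Section 11.4.3) and a 7-day Phase 2 (Section 8.2.1). 0.80 × 7 = 5.6 days, an exact match.

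**2. How the plan counts days.** Visit 2 is Day 1, Visit 6 is Day 14, and the study is described as 14 days long. Subtraction gives 14 − 1 = 13; inclusive counting gives 14 − 1 + 1 = 14. The plan therefore counts inclusively. By the same rule Phase 2 is 14 − 8 + 1 = 7 days, as Section 8.2.1 states. The 6-day figure comes from subtraction, which is not the plan's convention.

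**3. The visit windows.** Visit 4 may fall on Day 7, 8 or 9 and Visit 6 on Day 13, 14 or 15. Inclusive length L = Visit 6 day − Visit 4 day + 1.

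| Visit 4, Visit 6 days | L (days) | 80% of L | 5.6 / L |
|---|---|---|---|
| 9, 13 | 5 | 4.0 | 112% |
| 8, 13 and 9, 14 | 6 | 4.8 | 93.3% |
| 7, 13; 8, 14; 9, 15 | 7 | 5.6 | 80% |
| 7, 14 and 8, 15 | 8 | 6.4 | 70% |
| 7, 15 | 9 | 7.2 | 62.2% |

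The two forms coincide in 3 of 9 pairs, including the scheduled one. In 1 of 9 (late Visit 4, early Visit 6) 5.6 days cannot be reached. On elapsed time (Visit 6 day − Visit 4 day) the lengths run from 4 to 8 days, the scheduled pair gives 6 days (5.6 / 6 = 93.3%), and 3 of 9 pairs fall below 5.6 days: 8 to 13, 9 to 13 and 9 to 14. The documents do not say how often visits will fall on these days.

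**4. Which form governs.** The percentage is stated as the minimum. The day figure follows in parentheses, is marked as approximate, and equals 80% of the nominal phase. The ordinary reading is that 80% governs and 5.6 days illustrates it. On that reading no fully adherent subject is excluded for visit timing under any of the nine pairs.

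**5. What system use covers.** Section 2.1 lists the system's components as controller, Pod and CGM. Sections 8.2.1 and 11.4.2 define Phase 2 as Manual Mode with a connected CGM. Use of the system during Phase 2 therefore most naturally means Pod and connected CGM in Manual Mode. Section 12.2.1 stores insulin delivery and connected-CGM readings, and Section 3 says the data portal reports time in each mode, so the measure can be built from planned data.

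**6. Size of an Automated Mode lapse.** The documents give no inputs, so these are assumptions. Let f be the share of one subject's post-bolus records affected, from 1/42 (4 of 168 hours) to 2/7. Let D be the effect on those records: 5 to 15 points for time above 180 mg/dL, and 0.5 to 2 points for time below 70 mg/dL. The shift in a mean of n subjects is f × D / n. For the 6 to 70 report, n = 15 + 10 = 25.

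- Above 180: from (1/42 × 5) / 25 = 0.119 / 25 = 0.005 to (2/7 × 15) / 25 = 4.29 / 25 = 0.17 points.
- Below 70: from (1/42 × 0.5) / 25 = 0.012 / 25 = 0.0005 to (2/7 × 2) / 25 = 0.571 / 25 = 0.023 points.

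In the 5-subject cohort the upper ends are 4.29 / 5 = 0.86 and 0.571 / 5 = 0.11 points.

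**The case for a change.** The best case for a change rests on Automated Mode. The CGM is connected to the system only in Phase 2, so any Automated Mode use would fall there. Section 2.1 expects automated delivery to reduce both low glucose and meal-related high glucose. The error would therefore run one way and favour the CGM-informed calculator on both primary endpoints. The PP text leaves exclusion for it to judgment, and the upper figure for the 5-subject cohort is not trivial.

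The direction of that argument stands, and so does the observation that Section 11.4.3 does not name Automated Mode. But the protocol forbids such use, calls any instance a deviation and requires it to be documented. Automated delivery in a study confined to Manual Mode is a plain case of non-compliance that may confound the objective data, and the medication example does not close that category. The exclusion list is fixed before analysis, which limits selective choice. The upper figures assume two days' worth of Automated Mode in seven with the largest assumed effect.

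It also stands that system use has no written numerator, denominator or data source, and that the two forms part company when the windows change the phase length. Both are gaps in detail, and the plan's definition of Phase 2 and its stated percentage point to one sensible reading.

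The lack of a Phase 1 use threshold is a design preference. The major-deviation clause refers to the study's objective data, so serious Phase 1 non-compliance can still lead to exclusion.

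**Conclusion.** The two figures agree for Phase 2 as the plan schedules and counts it. They diverge only when the visit windows alter its length. On the plan's count 5.6 days is then unreachable in 1 of 9 day pairs, and that matters only if the approximate figure is allowed to override the 80%. What remains is undefined detail in a supportive analysis set: what counts as system use, over what time, and the unnamed but covered case of Automated Mode.

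Analysts can fill this from the plan's own description of Phase 2 and the stored device data when they draw up the exclusion list. The primary mITT results do not depend on it. The conclusion rests on reading 80% as the governing figure and on Automated Mode use being rare and recorded as a deviation. The bound of 0.17 points (above 180 mg/dL) and 0.023 points (below 70 mg/dL) per affected subject among 25 rests on assumed inputs. In a non-powered study without hypotheses or clinical claims, a clearer sentence would be tidier but would not alter what the study can conclude. No change is needed.

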11.5 Analysis of Primary and Secondary Endpoints

There are no hypotheses associated with any of the primary or secondary endpoints. Summary statistics will be presented by age cohort for all endpoints, stratified by time points of interest (e.g., day vs. night, overall). The primary and secondary endpoints will be summarized for modified Intention to Treat (mITT)

and Per Protocol (PP) analysis sets. If the PP analysis set does not differ from the MITT analysis set, separate analyses will not be presented. The data may be stratified by phase of the study, where the data collected during Phase 2 of the study will be compared to the data collected during Phase 1 of the study.

All statistical comparisons will be conducted at a two-sided significance level of 5% using a paired t-test or two sample t-test, as appropriate. If the assumptions for parametric test are grossly violated, a non-parametric method such as Wilcoxon signed rank test may be used. Since the results of endpoint analyses will not be used to support clinical claims, no adjustment for multiplicity will be performed.

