11 STATISTICAL CONSIDERATIONS

11.1 General Statistical Methods

Standard statistical methods will be employed to analyze all data. All data collected in this study will be documented using summary tables and subject data listings. Continuous variables will be summarized using descriptive statistics, including counts, mean, median, standard deviation (SD), minimum and maximum. Where appropriate, 95% two-sided confidence intervals for the means or medians will be presented. If the observed data are found not to follow a normal distribution, appropriate non-parametric methods may be employed. Categorical variables will be summarized by frequencies and percentages. Unless explicitly stated otherwise, percentages will utilize a denominator corresponding to the number of unique subjects.

Data from different centers will be pooled for all analyses. Data will be summarized by age cohort.

As subjects aged 6-70 years are expected to complete the study prior to the start of enrollment of subjects aged 2-5.9 years, two separate clinical reports will be generated.

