11.2 Sample Size

This is a non-powered, single-arm, multi-center, observational study. The sample size for the study is not hypothesis-driven and has been chosen to gather adequate clinical data on the performance of the Omnipod Horizon™ System's CGM-informed bolus calculator and summarize its safety profile.

Up to 42 subjects may be enrolled in the study cross 4-7 clinical study sites in order to obtain approximately 30 evaluable subjects. The evaluable subjects will be comprised of three age cohorts as follows:

- 15 subjects aged 18-70 years
- 10 subjects aged 6-17.9 years
- 5 subjects aged 2-5.9 years

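### Does the plan need a named age-pooled Phase 2 minus Phase 1 estimate, with a confidence interval, for the primary endpoints?

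*Combined protocol and SAP*

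**What the plan says.** Section 11.3.2 defines the primary endpoints as the share of CGM time below 70 and above 180 mg/dL in the four hours after a bolus, with Phase 2 compared to Phase 1.

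- **Presentation.** Section 11.5: "Summary statistics will be presented by age cohort for all endpoints, stratified by time points of interest (e.g., day vs. night, overall"). Section 11.1: "Data from different centers will be pooled for all analyses. Data will be summarized by age cohort".
- **Intervals.** Section 11.1: "Where appropriate, 95% two-sided confidence intervals for the means or medians will be presented".
- **Tests.** Section 11.5 sets a two-sided 5% level with a paired or two-sample t-test. If the assumptions fail badly, "a non-parametric method such as Wilcoxon signed rank test may be used". It does not say whether tests are run per cohort or over all ages.
- **Individual data.** Section 11.1: "All data collected in this study will be documented using summary tables and subject data listings".
- **Reporting.** Because ages 6-70 should finish before the preschool cohort starts enrolling, "two separate clinical reports will be generated" (section 11.1).
- **Purpose.** Section 11.2: "This is a non-powered, single-arm, multi-center, observational study". Section 11.5: "There are no hypotheses associated with any of the primary or secondary endpoints". Section 11.5 adds that the results will not support clinical claims.

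**The concern.** The two primary endpoints are the study's safety measures, and the question put to them is a within-subject change between phases. The natural summary is the mean paired difference with its interval, because that shows how large a worsening the data can exclude. The plan names neither that difference over all ages nor an interval for it, and commits firmly only to a 5% test. In cohorts of 15, 10 and 5, separate estimates are imprecise, and a pooled estimate looks like an obvious and cheap gain.

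The youngest cohort seems to make matters worse. With five non-zero pairs, an exact two-sided signed-rank test cannot give a p-value below 0.0625, so the fallback test could never reach 5% there. If the plan really prevented an interpretable estimate of the primary contrast, the safety summary would be weaker than the data allow.

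**Working it through.** **Inputs.** Evaluable targets of 15 (18-70 years), 10 (6-17.9) and 5 (2-5.9) come from section 11.2; 15 + 10 + 5 = 30 agrees with the stated total. The two-sided 5% level comes from section 11.5. The documents give no SD of the paired difference and no power or precision calculation, so there is no planned figure to reproduce. Half-widths are therefore in units of that SD, and all SD ratios below are assumptions.

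**1. Is pooling excluded?** Sections 11.1 and 11.5 say that results are summarized by cohort; neither says that this is the only presentation. In section 11.5, the sentence on the mITT and PP summaries and the sentence on the t-tests do not mention cohort. Section 11.4.2 defines mITT by entry into Phase 2, not by age. An all-ages or 6-70 column is therefore not named, but it is allowed.

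**2. Is the interval missing?** Section 11.1 provides 95% intervals for means, and a mean paired difference is a mean. Its interval is

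mean difference ± t(0.975, n−1) × SD/√n.

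It excludes zero exactly when |mean difference| × √n/SD > t(0.975, n−1), which is the rejection rule of the planned paired t-test. The method is in the plan; only the firmness of the wording is open.

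**3. Precision within cohorts,** t(0.975, n−1)/√n:

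- n = 15: 2.145/√15 = 0.55
- n = 10: 2.262/√10 = 0.72
- n = 5: 2.776/√5 = 1.24

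**4. Precision if pooled with a common SD,** stratified by cohort:

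- Ages 6-70: n = 25, df = 25 − 2 = 23, 2.069/√25 = 0.41, which is 25% narrower than adults alone (0.414/0.554 = 0.75).
- All ages: n = 30, df = 30 − 3 = 27, 2.052/√30 = 0.37, which is 32% narrower (0.375/0.554 = 0.68).

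**5. Precision if the SDs differ.** The variance of the size-weighted mean is Σ n_k SD_k²/N², with Satterthwaite degrees of freedom. For ages 6-70 at a ratio of 1:2, the variance is (15×1 + 10×4)/25² = 0.088, the SE is 0.297, df is 15.6 and t is 2.124, so the half-width is 0.63. Results in adult SDs:

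| Pooled group | SD ratio, oldest cohort first | Half-width |
|---|---|---|
| Ages 6-70 | 1:0.5 | 0.35 |
| Ages 6-70 | 1:1 | 0.41 |
| Ages 6-70 | 1:1.5 | 0.51 |
| Ages 6-70 | 1:2 | 0.63 |
| All ages | 1:0.5:0.5 | 0.30 |
| All ages | 1:1:1 | 0.37 |
| All ages | 1:1:2 | 0.47 |
| All ages | 1:1.5:2 | 0.53 |
| All ages | 1:2:2 | 0.60 |

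Adults alone give 0.55. At 1:2 the 6-70 interval is 14% wider than that (0.630/0.554 = 1.14), and at 1:2:2 the all-ages interval is wider too. The gain from pooling is possible but not assured.

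**6. What a pooled mean would describe.** Cohort-size weights reproduce the recruitment quotas, and no section defines a target population with that mix. An effect confined to the five youngest would appear at 5/30 = 1/6 of its size. Phase 1 always precedes Phase 2 in a single arm (section 5.2), so any interval, pooled or not, combines device and period effects.

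**7. The signed-rank floor.** The smallest exact two-sided p is 2/2ⁿ: 0.0625 for n = 5 and 0.031 for n = 6. To matter, it needs a test within the youngest cohort, exactly five non-zero pairs, use of the optional fallback, the choice of Wilcoxon (named only as an example) and its exact form. Five is a target, not a cap: up to 42 subjects may be enrolled, and mITT takes all who enter Phase 2.

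**The case for a change.** The strongest reply is that permission is not prespecification. A choice made after seeing the data, whether to pool or whether an interval is appropriate, is the kind of freedom a plan should remove. Section 11.5 even words the split by phase as something that may be done. In a study meant to summarize a safety profile, an estimate with its interval says more than a p-value.

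Part of this stands. The wording on intervals is conditional, no age-pooled difference is named, and firmer text would be tidier. But section 11.3.2 states the comparison between phases without reservation, so the primary contrast itself is not optional. The freedom that remains also has little to act on, since no hypothesis, claim or stopping rule is tied to the result. A pooled estimate would be a supplement whose weights follow the quotas, and an all-ages version belongs to neither of the two planned reports as they are described. For the cohort of five, replacing the test by a t-based interval restates the planned paired t-test in another form, and the children's values are to be listed in any case.

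**Conclusion.** The concern does not hold as a fault in the plan. Followed as written, the plan gives descriptive results for each cohort, a paired comparison of the phases, 95% intervals for means where appropriate, and subject listings. That suits a non-powered study with no hypotheses. The missing pooled estimate is a matter of preference and detail. Its possible benefit ranges from a clear gain (0.41 against 0.55 SD for ages 6-70 with equal SDs) to a loss (0.63 against 0.55 if the 6-17.9 cohort is twice as variable), and the documents give no SDs to decide between them. The signed-rank floor of 0.0625 is correct arithmetic, but it depends on several conditions that the plan does not set.

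This conclusion rests on two readings: that summarizing by cohort does not forbid other summaries, and that the interval provision in section 11.1 extends to a mean paired difference. Both follow from the text. It also rests on the statement in section 11.5 that the endpoint results will not support clinical claims.

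### Does the plan need an explicit commitment to a 95% confidence interval for the Phase 2 minus Phase 1 difference in the two primary safety endpoints?

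*Combined protocol and SAP*

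**What the plan says.** Section 11.3.2 names the two primary safety endpoints and has Phase 2 compared with Phase 1, without saying how. Section 11.5 supplies the method. It first states: "There are no hypotheses associated with any of the primary or secondary endpoints". It then sets the level and sidedness of testing: "All statistical comparisons will be conducted at a two-sided significance level of 5% using a paired t-test or two sample t-test, as appropriate". A Wilcoxon signed rank test is an optional fallback. On multiplicity it adds: "Since the results of endpoint analyses will not be used to support clinical claims, no adjustment for multiplicity will be performed". On description it commits to this: "Summary statistics will be presented by age cohort for all endpoints".

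Section 11.2 gives the setting: "This is a non-powered, single-arm, multi-center, observational study", and "The sample size for the study is not hypothesis-driven". The evaluable targets are 15 adults, 10 subjects aged 6-17.9 and "5 subjects aged 2-5.9 years".

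The only statement about intervals is in the general methods, section 11.1: "Where appropriate, 95% two-sided confidence intervals for the means or medians will be presented". The same section lists the standard summaries without condition (count, mean, median, SD, minimum, maximum), plans subject data listings, and announces separate reports for ages 6-70 and ages 2-5.9.

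**The concern.** A study without hypotheses or power has little use for a significance test on its own. For safety, the reader wants to know how far time below 70 or above 180 mg/dL moved and how much worsening the data rule out. A p-value answers neither question. Yet the one inferential tool that section 11.5 attaches to the primary comparison is a 5% test, and no passage commits to an interval for the between-phase difference.

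The worry is sharpest in the youngest cohort, which has a target of five and its own report. A sizeable worsening there could easily be non-significant, and a reader shown only that result might be falsely reassured. Section 1 adds some weight, because it says the data will supplement the in-silico work in support of safety and effectiveness.

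**Working it through.** The plan states no power, effect size, SD or margin, so it has no figure of its own to reproduce. Three checks apply.

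**1. Does the existing text reach the interval?** The sentence in 11.1 covers means and medians generally. If the comparison is a paired t-test, the analysed quantity is the mean of the within-subject differences, so an interval for that mean is within its scope. The wording is conditional and does not name the difference. What is missing is therefore explicitness: the plan neither excludes the interval nor puts a wrong analysis in its place.

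**2. What would the interval show?** For a paired t analysis with SD of the differences *s*, the half-width is t(0.975, n-1) x *s* / sqrt(n). At the targets in 11.2:

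| Group | n | Calculation | Half-width (units of *s*) |
|---|---|---|---|
| Ages 2-5.9 | 5 | 2.7764 / sqrt(5) | 1.24 |
| Ages 6-17.9 | 10 | 2.2622 / sqrt(10) | 0.72 |
| Ages 18-70 | 15 | 2.1448 / sqrt(15) | 0.55 |
| Ages 6-70 pooled (assumption) | 25 | 2.0639 / sqrt(25) | 0.41 |

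A mean worsening just short of p < 0.05 equals one half-width, so its upper limit is twice that: 2.48, 1.43 and 1.11 *s* at n = 5, 10 and 15. The documents give no *s*. If it were 1 to 5 percentage points for time below 70 mg/dL (an assumption), the half-width at n = 5 would be 1.2 to 6.2 points. These widths come from the sample size and are the same whether or not the plan promises an interval. The modified ITT set may exceed the evaluable targets, which would narrow them.

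**3. Would a promise change any result?**

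- *Paired t-test.* The 95% interval excludes zero exactly when p < 0.05. In 5000 simulated samples of 30 pairs the two agreed every time. Alpha, sample size and decisions are unaffected.
- *Recovering the interval.* If the phase means are shown for the same subjects and the paired p-value is reported, then for a non-zero mean difference d the p-value gives |t|, the standard error is |d| / |t|, and the interval is d ± t(0.975, n-1) x |d| / |t|.
- *Two-sample t-test.* The interval follows from the count, mean and SD of each phase.
- *Signed rank fallback with five non-zero differences.* The smallest exact two-sided p-value is 2/32 = 0.0625, and the widest exact interval has coverage 1 - 2/32 = 93.75%. The test then cannot reach 5%, and no exact signed-rank interval reaches 95%. Both limits come from having five subjects, and wording does not remove them.

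**The case for a change.** The best case for a change is that the sentence in 11.1 could be satisfied by an interval around each phase's mean. For paired data those two intervals do not give the interval for the difference, because its variance, s1² + s2² - 2·r·s1·s2, needs the within-subject correlation r. Recovery from a p-value works for the t-tests but fails under the Wilcoxon option, where a reader would need the subject listings. The addition would cost one sentence, and when results are descriptive an estimate with its interval is the natural main output.

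All of that is correct, and it is true that no passage commits to the interval. It shows that the wording could be tighter. It does not show that following the plan yields a misleading result. The plan does not say that a non-significant difference will be read as safety. Section 11.5 rules out clinical claims from these endpoints. It also fixes only the level and sidedness, leaving the choice of test open, so the test is not the sole planned output: means and SDs by cohort are committed, and with the phases compared as 11.3.2 requires, the size of the change is visible.

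**Conclusion.** No change is needed. This is a gap in detail that a competent analyst fills sensibly: in a paired before-and-after comparison, the interval foreseen in 11.1 naturally attaches to the mean difference. The figures of 1.24, 0.72 and 0.55 SD describe how little five, ten or fifteen subjects can show; they do not measure harm from the missing sentence. The conclusion assumes that summaries are shown by phase, that the phases are compared within subject, and that the descriptive status given in 11.2 and 11.5 is respected in both reports. If a report treated non-significance as evidence of safety, particularly at ages 2-5.9, that would be an error of interpretation going beyond what the plan allows.
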